Appendix C Prochaska “Stage of Change” Questionnaire

The Prochaska questionnaire is structured as follows:

Confidentiality Statement

Data and information contained in this document are considered to constitute trade secrets and confidential commercial information, and the legal protections provided to such trade secrets and confidential information are hereby claimed under the provisions of applicable law. No part of this document may be publicly disclosed without the written consent of Philip Morris Products S.A.

The questionnaire to be asked is as follows, with the scoring sheet not to be read aloud:

Smoking algorithm for the classification of the stages of change for smoking cessation

Assessment:

1. Are you currently a smoker?
 - A) Yes, I currently smoke
 - B) No, I quit within the last 6 months
 - C) No, I quit more than 6 months ago
 - D) No, I have never smoked

Smokers only:

2. In the last year, how many times have you quit smoking for at least 24 hours? ____
3. Are you seriously thinking of quitting smoking?
 - A) Yes, within the next 30 days
 - B) Yes, within the next 6 months
 - C) No, not thinking of quitting

Scoring Sheet (do not read to subject):

1. Are you currently a smoker?
 - A) Yes, I currently smoke
 - B) No, I quit within the last 6 months (ACTION STAGE)
 - C) No, I quit more than 6 months ago (MAINTENANCE STAGE)
 - D) No, I have never smoked (NONSMOKER)

Smokers only:

2. In the last year, how many times have you quit smoking for at least 24 hours? -----
3. Are you seriously thinking of quitting smoking?
 - A) Yes, within the next 30 days (PREPARATION STAGE if they have one 24-hour quit attempt in the past year, if there was no quit attempt in the past year, then CONTEMPLATION STAGE)
 - B) Yes, within the next 6 months (CONTEMPLATION)
 - C) No, not thinking of quitting (PRECONTEMPLATION)

Confidentiality Statement

Data and information contained in this document are considered to constitute trade secrets and confidential commercial information, and the legal protections provided to such trade secrets and confidential information are hereby claimed under the provisions of applicable law. No part of this document may be publicly disclosed without the written consent of Philip Morris Products S.A.

Appendix D Summary of Biomarkers of Exposure to HPHC

HPHC ^[smoke phase]	HPHC List	Biomarker	Matrix	t _{1/2}
1,3-Butadiene [gas]	FDA-18, FDA-93, HC PMI-58, WHO-18	Monohydroxybutenylme rcapturic acid (MHBMA)	Urine	4 to 16 h
1-Aminonaphthalene [particulate]	FDA-18, FDA-93, HC PMI-58	1-Aminonaphthalene (1- NA)	Urine	Not described
2-Aminonaphthalene [particulate]	FDA-18, FDA-93, HC PMI-58, WHO-18	2-Aminonaphthalene (2- NA)	Urine	9 h
4-Aminobiphenyl [particulate]	FDA-18, FDA-93, HC PMI-58, WHO-18	4-Aminobiphenyl (4-ABP)	Urine	26 h
4-(methylnitrosamino)- 1-(3-pyridyl)-1- butanone (NNK) [particulate]	FDA-18, FDA-93, HC PMI-58, WHO-18	Total 4- (methylnitrosamino)-1- (3-pyridyl)-1-butanol (total NNAL)	Urine	10 to 18 days
Acrolein [gas]	FDA-18, FDA-93, HC PMI-58, WHO-18	3-Hydroxypropyl- mercapturic acid (3-HPMA)	Urine	10 h
Acrylonitrile [gas]	FDA-18, FDA-93, HC PMI-58, WHO-18	2- Cyanoethylmercapturic acid (CEMA)	Urine	17 h
Benzene [gas]	FDA-18, FDA-93, HC PMI-58, WHO-18	S-Phenylmercapturic acid (S-PMA)	Urine	9 to 15 h
Benzo[a]pyrene [particulate]	FDA-18, FDA-93, HC PMI-58, WHO-18	3- Hydroxybenzo[a]pyrene B[a]P	Urine	3 to 4 h

Confidentiality Statement

Data and information contained in this document are considered to constitute trade secrets and confidential commercial information, and the legal protections provided to such trade secrets and confidential information are hereby claimed under the provisions of applicable law. No part of this document may be publicly disclosed without the written consent of Philip Morris Products S.A.

HPHC ^[smoke phase]	HPHC List	Biomarker	Matrix	t _{1/2}
Carbon monoxide [gas]	FDA-18 FDA-93 HC PMI-58 WHO-18	CO	Breath	/
Pyrene	FDA-18 FDA-93 HC PMI-58 WHO-18	Total 1-hydroxypyrene (Total 1-OHP)	Urine	6 to 35 h
Crotonaldehyde [gas]	FDA-18, FDA-93, HC PMI-58, WHO-18	3-Hydroxy-1- methylpropyl- mercapturic acid (3- HMPMA)	Urine	2 days
Ethylene oxide [gas]	FDA-93, PMI-58	2-Hydroxyethyl- mercapturic acid (HEMA)	Urine	5 h
NNN [particulate]	FDA-18, FDA-93, HC PMI-58, WHO-18	Total N- nitrosonornicotine (total NNN)	Urine	15 h
o-Toluidine [gas]	FDA-93, PMI-58	o-Toluidine (o-TOL)	Urine	10 to 16 h
Nicotine [particulate]	FDA-18, FDA-93, HC PMI-58	Nicotine (NIC-P)	Plasma	1 to 2 h
		Cotinine (COT-P) 3-OH Cotinine (3-OHCOTP)	Plasma	16 to 18 h -
		Nicotine equivalents (Neq)	Urine	16 h (estimated)

Confidentiality Statement

Appendix E Abnormal Laboratory Values

ABNORMAL LABORATORY VALUES RATING: SERUM CHEMISTRY PARAMETERS

Serum Chemistry *	Mild (Grade 1)	Moderate (Grade 2)	Severe (Grade 3)	Life-Threatening (Grade 4)
Sodium – Hyponatremia ^[49] (mmol/L)	< LLN - 130	-	< 130 - 120	< 120
Sodium – Hypernatremia ^[49] (mmol/L)	> ULN - 150	> 150 - 155	> 155 – 160 hospitalization indicated	> 160
Potassium – Hyperkalemia ^[49] (mmol/L)	> ULN - 5.5	> 5.5 - 6.0	> 6.0 - 7.0 hospitalization indicated	> 7.0
Potassium – Hypokalemia ^[49] (mmol/L)	< LLN - 3.0	< LLN - 3.0; symptomatic; intervention indicated	< 3.0 - 2.5 hospitalization indicated	< 2.5
Glucose – Hypoglycemia ^[49] (mg/dL) (mmol/L)	< LLN – 55 < LLN – 3.0	< 55 – 40 < 3.0 – 2.2	< 40 – 30 < 2.2 – 1.7	< 30; < 1.7
Glucose – Hyperglycemia ^[49] Fasting (mg/dL) (mmol/L)	> ULN - 160 > ULN - 8.9	> 160 - 250 > 8.9 - 13.9	> 250 - 500 > 13.9 - 27.8 hospitalization indicated	> 500 > 27.8
Creatinine increased ^[49]	> 1 – 1.5 x Baseline > ULN – 1.5 x ULN	> 1.5 – 3.0 x Baseline > 1.5 – 3.0 x ULN	> 3.0 x Baseline > 3.0 – 6.0 x ULN	> 6.0 x ULN
Albumin - Hypoalbuminemia ^[49] (g/dL) (g/L)	< LLN – 3 < LLN - 30	< 3 – 2 < 30 - 20	< 2 < 20	-
Alkaline phosphatase increased ^[49]	> ULN – 2.5 x ULN	> 2.5 – 5.0 x ULN	> 5.0 – 20.0 x ULN	> 20.0 x ULN
ALT/AST increased ^[49]	> ULN – 3.0 x ULN	> 3.0 – 5.0 x ULN	> 5.0 – 20.0 x ULN	> 20.0 x ULN

Confidentiality Statement

Data and information contained in this document are considered to constitute trade secrets and confidential commercial information, and the legal protections provided to such trade secrets and confidential information are hereby claimed under the provisions of applicable law. No part of this document may be publicly disclosed without the written consent of Philip Morris Products S.A.

Serum Chemistry *	Mild (Grade 1)	Moderate (Grade 2)	Severe (Grade 3)	Life-Threatening (Grade 4)
Gamma-glutamyl transferase (GGT) increased ^[49]	> ULN – 2.5 x ULN	> 2.5 – 5.0 x ULN	> 5.0 – 20.0 x ULN	> 20.0 x ULN
Blood bilirubin increased ^[49] (total and direct)	> ULN – 1.5 x ULN	> 1.5 – 3.0 x ULN	> 3.0 – 10.0 x ULN	> 10.0 x ULN
Cholesterol high ^[49] (mg/dL) (mmol/L)	> ULN - 300 > ULN - 7.75	> 300 - 400 > 7.75-10.34	> 400 - 500 > 10.34-12.92	> 500 > 12.92
Triglycerides – Hypertriglyceridemia ^[49] (mg/dL) (mmol/L)	150 – 300 1.71 – 3.42	> 300 – 500 > 3.42 – 5.70	> 500 – 1000 > 5.70 – 11.40	> 1000 > 11.4

Abbreviations: ALT = Alanine aminotransferase; AST = Aspartate aminotransferase; BUN = Blood urea nitrogen; GGT = Gamma-glutamyl transferase; LLN = Lower limit of the normal range; ULN = Upper limit of the normal range.

* Those parameters that are not listed do not have grading categories in the CTCAE will be reviewed by the Principal Investigator and only reported as an AE if considered to be clinically significant.

Confidentiality Statement

Data and information contained in this document are considered to constitute trade secrets and confidential commercial information, and the legal protections provided to such trade secrets and confidential information are hereby claimed under the provisions of applicable law. No part of this document may be publicly disclosed without the written consent of Philip Morris Products S.A.

ABNORMAL LABORATORY VALUES RATING: HEMATOLOGY PARAMETERS

Hematology*	Mild (Grade 1)	Moderate (Grade 2)	Severe (Grade 3)	Life- Threatening (Grade 4)
Anemia (hemoglobin) (g/dL) (mmol) g/L	< LLN-10.0 < LLN-6.2 < 100	< 10-8.0 < 6.2-4.9 < 100-80	< 8.0 < 4.9 < 80 Transfusion indicated	Life threatening consequences; urgent intervention indicated
Hemoglobin increase ^[49] (g/dL)	Increase in > 0 – 2 above ULN or above Baseline if Baseline is above ULN	Increase in > 2 – 4 above ULN or above Baseline if Baseline is above ULN	Increase in > 4 above ULN or above Baseline if Baseline is above ULN	-
WBC decrease ^[49] (cell/mm ³) 10 ⁻⁹ /l	< LLN – 3000 < LLN – 3.0	< 3000 – 2000 < 3.0 – 2.0	< 2000 - 1000 < 2.0 – 1.0	< 1000 < 1.0
Lymphocytes increase ^[49] (cell/mm ³)	-	> 4,000 – 20,000	> 20,000	-
Lymphocytes decrease ^[49] (cell/mm ³) 10 ⁻⁹ /l	< LLN – 800 < LLN – 0.8	< 800 - 500 < 0.8 – 0.5	< 500 - 200 < 0.5 – 0.2	< 200 < 0.2
Neutrophils decrease ^[49] (cell/mm ³) 10 ⁻⁹ /l	< LLN – 1500 < LLN – 1.5	< 1500 - 1000 < 1.5 – 1.0	< 1000 - 500 < 1.0 – 0.5	< 500 < 0.5
Platelets decrease ^[49] (cell/mm ³) 10 ⁻⁹ /l	< LLN – 75,000 < LLN – 75.0	< 75,000 – 50,000 < 75.0 – 50.0	< 50,000 – 25,000 < 50.0 – 25.0	< 25,000 < 25.0

Abbreviations: LLN = Lower limit of the normal range; ULN = Upper limit of the normal range; WBC = White blood cell.

* Those parameters that are not listed do not have grading categories in the CTCAE will be reviewed by the Principal Investigator and only reported as an AE if considered to be clinically significant.

Confidentiality Statement

Data and information contained in this document are considered to constitute trade secrets and confidential commercial information, and the legal protections provided to such trade secrets and confidential information are hereby claimed under the provisions of applicable law. No part of this document may be publicly disclosed without the written consent of Philip Morris Products S.A.

ABNORMAL LABORATORY VALUES RATING: URINALYSIS PARAMETERS

Urine *	Mild (Grade 1)	Moderate (Grade 2)	Severe (Grade 3)	Life-Threatening (Grade 4)
Protein ^[49]	1+ proteinuria; urinary protein < 1.0 g/24 hours	2+ proteinuria; urinary protein 1.0 - 3.4 g/24 hours	Urinary protein ≥ 3.5 g/24 hours	-

Abbreviations: ADL = Activities of daily living; IV = Intravenous.

* Those parameters that are not listed do not have grading categories in the CTCAE will be reviewed by the Principal Investigator and only reported as an AE if considered to be clinically significant.

Confidentiality Statement

Data and information contained in this document are considered to constitute trade secrets and confidential commercial information, and the legal protections provided to such trade secrets and confidential information are hereby claimed under the provisions of applicable law. No part of this document may be publicly disclosed without the written consent of Philip Morris Products S.A.

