8.4 Abnormal Results of Laboratory Tests

Any clinical safety laboratory test result that is outside of the normal reference range will be reviewed by the PI and assessed for clinical significance according to its severity. A clinically significant abnormal laboratory test result detected at the Screening Visit must be recorded as a concomitant disease. A clinically significant abnormal laboratory test result detected after the Screening Visit, but within the Screening Period, must be recorded as a concomitant disease or an AE based on the judgement of the PI. A clinically significant abnormal result detected after the Screening Period must be recorded as an AE (or linked to a concomitant disease), and handled according to the directions in sections 8.2 and 8.3. The severity of AEs representing clinically significant abnormal laboratory results should be assessed using the grading scheme shown in [Appendix E](#). Whenever that grading scheme is not available for the laboratory result of concern, the PI should assess the severity and the clinical significance of that result using his/her medical judgment.

The principles for assessing and reporting abnormal laboratory test results, **emerging after the Screening Period**, using the grading scheme shown in [Appendix E](#), is the following:

- All **Grade 1** abnormal laboratory value will be evaluated by the Investigator taking into account the value of the test of concern at Baseline and its clinical significance. If

Confidentiality Statement

Data and information contained in this document are considered to constitute trade secrets and confidential commercial information, and the legal protections provided to such trade secrets and confidential information are hereby claimed under the provisions of applicable law. No part of this document may be publicly disclosed without the written consent of Philip Morris Products S.A.

considered to be clinically significant, the Investigator must report it as an AE, or link it to a reported AE or to a concomitant disease.

- All **Grade 2** and higher abnormal laboratory value must be reported as an AE, or linked to an AE or a concomitant disease.

If there is any **worsening** in grade, the Investigator must report this worsening as an AE.

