12.5.4.3 Clinical Laboratory Evaluation

Table 18 below lists the hematology, clinical chemistry and urine analysis parameters to be assessed in this study.

Table 18: List of Laboratory Safety Parameters		
Hematology	Clinical Chemistry	Urine Analysis
Hematocrit	Albumin	pH
Hemoglobin	Total protein	Bilirubin
Mean corpuscular hemoglobin	Alkaline phosphatase	Glucose
Mean corpuscular hemoglobin concentration	Alanine aminotransferase	Nitrite
Mean corpuscular volume	Aspartate aminotransferase	Red blood cell traces
Platelet count	Blood urea nitrogen	Protein
Red blood cell count	Creatinine	Specific gravity
White blood cell (WBC) count	Gamma-glutamyl transferase	Urine sediment
Differential WBC count:	Fasting glucose	
• Neutrophils	Lactate dehydrogenase	
• Basophils	Potassium	
• Eosinophils	Sodium	
• Lymphocytes	Total bilirubin	
• Monocytes	Direct bilirubin	
	Total cholesterol	
	Triglycerides	

Any clinical safety laboratory test result that is outside of the normal reference range will be reviewed by the PI and assessed for clinical relevance. If the PI considers the abnormal result to be of clinical relevance, then it must be recorded as a concomitant disease at Screening, or if not present at Screening, as an AE during the study. If the condition worsens from screening to after product-use it will be recorded as an AE.

The grading scheme used in the Common Terminology Criteria for Adverse Events and Common Toxicity Criteria [CTCAE] version 4.03) will be used by the PI to assess abnormal laboratory AEs. These CTCAE grades will be derived programmatically in the creation of the datasets.

Laboratory data will be summarized (Table 15.2.6.11-13) and listed by arm, subject and parameter, at Screening and Day -1 for the Pre-Randomization period and at Day 6, Day

30 Visit, Day 60 Visit and Day 90 Visit for the Randomized period, together with numerical changes from baseline (Listing 15.3.6.2 - Listing 15.3.6.4). The number and percentage of subjects with normal results, high/low results, abnormal clinical result (as defined by PI comment) and with shift in normality and shift in toxicity grading from baseline will be tabulated for laboratory parameters.

[figure not shown]

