Listings for the clinical laboratory data will include the following information: normal/high/low (with respect to the reference range), abnormal clinically relevant (as defined by the PI comments), the PI comments, the change from baseline, the CTCAE grade and the shift in normality and shift in toxicity. Only CTCAE grades of 1 or more will be presented.

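### Grade 1 serum creatinine has no upper-limit-of-normal condition, so the programmed toxicity shift will grade in-range random variation and the Grade 1 row will carry no information

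*Protocol*

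**What the plan says.** Appendix E of the protocol gives two criteria for each of creatinine Grades 1 to 3, one relative to the subject's own baseline and one relative to ULN, with no connecting word printed between them. Grade 1 is "> 1 – 1.5 x Baseline > ULN – 1.5 x ULN" and Grade 2 is "> 1.5 – 3.0 x Baseline > 1.5 – 3.0 x ULN". No other row of the serum chemistry table refers to baseline. In the hematology table, the hemoglobin-increase row does refer to baseline, but with a condition: "above ULN or above Baseline if Baseline is above ULN".

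SAP 12.5.4.3 names the scale: "The grading scheme used in the Common Terminology Criteria for Adverse Events and Common Toxicity Criteria [CTCAE] version 4.03". Appendix E attributes its creatinine row to the same source (reference 49). The SAP goes on: "These CTCAE grades will be derived programmatically in the creation of the datasets". For output it promises that "shift in toxicity grading from baseline will be tabulated for laboratory parameters", and for the listings, "Only CTCAE grades of 1 or more will be presented". Protocol 12.5.4 also plans shift tables in toxicity grade.

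Under Protocol 8.4 a Grade 1 value becomes an adverse event only if the investigator judges it clinically significant. The same section then says of any worsening "in grade, the Investigator must report this worsening as an AE".

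**The concern.** The baseline part of the Grade 1 criterion is met by any value above the subject's own baseline, however small the difference and wherever both values lie in the reference range. To illustrate, 75 µmol/L on Day -1 followed by 76 µmol/L on Day 6 is a shift from no grade to Grade 1. The effect runs one way: a baseline value cannot exceed itself, so this criterion never grades it, while every later value can be graded.

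Clinical chemistry belongs to the safety objective (secondary objective 9). If the grading is programmed as printed, a large share of healthy subjects in both arms will appear with a creatinine toxicity grade that reflects only biological and assay variation. A reader of the shift table or listing could not tell those entries from real mild elevations.

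**Working it through.** The documents give no expected rate of creatinine grades, so there is no plan figure to reproduce.

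**1. How the two criteria combine.** Suppose both were required. A value at 1.6 x baseline and 1.2 x ULN would fail Grade 1 (above 1.5 x baseline) and also fail Grade 2 (not above 1.5 x ULN), so it would have no grade. Reading the criteria as alternatives leaves no such gap. That reading is used below.

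**2. Inputs from the documents.**
- Baseline is one value, the last valid one before first product use (SAP 12.1.4). For chemistry this is normally Day -1.
- There are four planned post-baseline panels: Day 6 and the Day 30, 60 and 90 Visits (SAP 12.5.4.3).
- 80 subjects are randomized to CHTP 1.2 and 40 to CC (Protocol 12.2).

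**3. Exact result for finely measured values.** With no true change, a subject's baseline and k later values are exchangeable. Then

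P(at least one later value above baseline) = 1 − P(baseline is the largest of k + 1) = k/(k + 1),

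whatever the size of the noise. For one visit this is 1/2 = 50%. For four visits it is 4/5 = 80%, that is 0.80 x 80 = 64 CHTP 1.2 subjects and 0.80 x 40 = 32 CC subjects. If each ambulatory visit is missed with probability 5–20%, the 80% falls only to 79–77%.

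**4. Effect of rounding.** Ties with baseline are not graded, so coarser reporting lowers the rate. The simulation used 300,000 subjects, with assumptions that are not in the documents: subject means about 75 µmol/L (SD 11) and within-subject CV 3–8%.

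| Reporting unit | Grade 1 at one visit | Grade 1 at least once in four |
|---|---|---|
| Continuous | 50% | 80% |
| 0.01 mg/dL | 44–48% | 75–78% |
| 1 µmol/L | 44–48% | 74–78% |
| 0.1 mg/dL | 14–31% | 30–59% |

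At 0.1 mg/dL the one-visit figure is about 19–31% if the CV is at least 4%.

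**5. Higher grades.** Noise alone takes a value above 1.5 x baseline in fewer than 0.1% of subjects over the four visits, so Grade 2 and above are not contaminated.

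**6. With a ULN condition.** With an assumed ULN of 106 µmol/L (not in the documents), noise-only Grade 1 over four visits falls to about 0.5–3% at fine reporting, or about 1–5% at 0.1 mg/dL.

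**The case against.** The best defence is that grading was meant for abnormal results only. Appendix E is titled for abnormal values, Protocol 8.4 starts from results outside the reference range, and SAP 12.5.4.3 introduces CTCAE as the investigator's tool for abnormal laboratory events before it mentions the programmed derivation. This shows a likely intention. It is not a rule that a programmer can apply: no sentence says that in-range values are left ungraded, and the creatinine row lacks the condition that the hemoglobin-increase row carries.

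It can also be said that the SAP cites CTCAE v4.03 rather than Appendix E, so the sponsor is using a cited standard scale. That is fair, and the external text cannot be checked here. But Appendix E presents its row as taken from that source, and it is the only wording the documents give.

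Other objections stand and limit the point:
- A reader might infer that a real creatinine signal would be hidden. The documents do not support that. SAP 12.5.4.3 separately tabulates high/low results, clinically abnormal results and shift in normality, and reports numerical change from baseline.
- A reader might take three quarters of subjects as the unconditional rate. That needs an any-visit summary and fine reporting units. The SAP summarizes laboratory data at named visits and does not say whether shifts are by visit or worst post-baseline.
- A reader might expect the adverse event tables to be inflated. Under Protocol 8.4 a Grade 1 value is an event only if clinically significant, so any increase depends on how sites resolve the conflict with the sentence on worsening.

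**Conclusion.** The point holds as a defect of one row in a descriptive safety output. Followed literally, the plan makes the Grade 1 creatinine entries of the toxicity shift table and listing uninformative. The share of subjects graded by noise alone is about 44–50% at a single visit and 74–80% over four visits at 1 µmol/L or 0.01 mg/dL, and about 14–31% and 30–59% at 0.1 mg/dL. These figures rest on no true change, on the two criteria being alternatives, on grading every value, and on the assumed CV and reporting precision. Only the 50% and 80% for continuous values are free of the last two assumptions.

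The artefact is the same in both arms, so it adds noise without favoring either product. The primary endpoints are untouched.

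The two sentences in Protocol 8.4 are a separate matter. For a move from no grade to Grade 1, one leaves reporting to clinical judgement and the other makes it mandatory.

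**What to change.** Add to SAP 12.5.4.3: *For the programmed tabulation and listing, creatinine values within the reference range and not more than 1.5 x baseline are shown as Grade 0, so that Grade 1 requires a value above ULN. The criteria for higher grades are unchanged.* It would help to state in the same place whether toxicity shifts are shown by visit or as worst post-baseline grade.

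The cost is one sentence and one line of derivation code, with no new data. There are two downsides. The tabulation departs, with documentation, from the literal grading text for one parameter. And an in-range value above 1.5 x baseline moves straight from Grade 0 to Grade 2; by the calculation above, noise alone should do this in fewer than 0.1% of subjects.

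The sponsor must reconcile the two sentences in Protocol 8.4; this review does not say which should prevail. If that changes the protocol text, Protocol 1.1 requires the amendment to go to the ethics committee, a cost that the SAP change does not carry.

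### In Protocol Appendix E the g/L line of the Grade 1 anemia cell is not a conversion of its g/dL and mmol lines, so a hemoglobin value graded in g/L can have no grade or two grades.

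*Protocol*

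**What the plan says.** The hematology table in Protocol Appendix E labels the row "Anemia (hemoglobin) (g/dL) (mmol) g/L", so each grade cell carries three lines in that unit order:

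- Grade 1: "< LLN-10.0 < LLN-6.2 < 100"
- Grade 2: "< 10-8.0 < 6.2-4.9 < 100-80"
- Grade 3: "< 8.0 < 4.9 < 80 Transfusion indicated"

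Protocol section 8.4 makes this table operative: "The severity of AEs representing clinically significant abnormal laboratory results should be assessed using the grading scheme shown in" Appendix E. For results arising after the Screening Period it then ties duties to the grade. A Grade 1 value is reported, or linked to an AE or concomitant disease, only if the investigator finds it clinically significant. A Grade 2 "and higher abnormal laboratory value must be reported as an AE, or linked to an AE or a concomitant disease". Any worsening in grade must be reported as an AE.

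SAP section 12.5.4.3 names CTCAE version 4.03 as the scheme for laboratory abnormalities and adds: "These CTCAE grades will be derived programmatically in the creation of the datasets". It plans shift tables of toxicity grade from baseline, and its listings show only grades of 1 or more. It does not restate the hemoglobin cut points and does not refer to Appendix E.

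**The concern.** Three unit lines in one cell should describe one range. Here the grade depends on which line is read, and on the g/L line the bands leave a gap and overlap.

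Three uses of the grade are exposed. First, the severity that the site records for a low hemoglobin. Second, the rule on worsening. For example, a fall from 95 to 75 g/L is a step from Grade 2 to Grade 3 on the specific bands, but no step at all if both values are read as Grade 1. Third, the boundary between Grade 1 and Grade 2, which is where section 8.4 moves from investigator discretion to mandatory reporting. In addition, a site grade taken from Appendix E and a programmed CTCAE 4.03 grade could differ for the same sample.

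**Working it through.** **Inputs.** The cut points are those of the Appendix E anemia row. The conversion is 1 g/dL = 10 g/L. The LLN is not given in either document, so it is assumed at 11.5, 12.0, 13.0 and 13.5 g/dL to show a range.

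**Step 1: convert each g/dL band and compare it with the printed g/L band.**

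| Grade | g/dL line × 10 | Printed g/L line | Agree? |
|---|---|---|---|
| 2 | below 10 × 10 = 100, down to 8.0 × 10 = 80 | below 100, down to 80 | yes |
| 3 | below 8.0 × 10 = 80 | below 80 | yes |
| 1 | below LLN, down to 10.0 × 10 = 100 | below 100, no lower end | no |

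The Grade 2 and Grade 3 lines reproduce exactly, so the g/L line is meant as a conversion. Only the Grade 1 line fails.

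**Step 2: grade sample values on each line as printed.**

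| Value | g/dL line | g/L line |
|---|---|---|
| 11.0 g/dL = 110 g/L (below every assumed LLN) | Grade 1 | none |
| 10.0 g/dL = 100 g/L | Grade 1 | none |
| 9.0 g/dL = 90 g/L | Grade 2 | Grades 1 and 2 |
| 7.0 g/dL = 70 g/L | Grade 3 | Grades 1 and 3 |

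Exactly 100 g/L falls in no g/L band. The overlap with Grade 2 therefore runs from 80 to just under 100 g/L.

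**Step 3: count discordant whole-number values from 60 g/L to just below the LLN.** There are 20 values from 60 to 79 (Grades 1 and 3 against 3) and 20 from 80 to 99 (Grades 1 and 2 against 2). To these are added the values from 100 to just below the LLN (none against Grade 1).

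| Assumed LLN | Discordant | Checked |
|---|---|---|
| 11.5 g/dL | 20 + 20 + 15 = 55 | 55 |
| 12.0 g/dL | 20 + 20 + 20 = 60 | 60 |
| 13.0 g/dL | 20 + 20 + 30 = 70 | 70 |
| 13.5 g/dL | 20 + 20 + 35 = 75 | 75 |

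Every value checked is discordant, whatever LLN is assumed. When the g/L line is given the same form as the other two lines of its cell, the count is 0 in all four cases. That is a consistency check, not a proposed threshold.

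**Step 4: compare other rows.** Albumin, hypoglycemia, WBC, lymphocyte decrease, neutrophils and platelets also carry two unit lines with an LLN bound at Grade 1. All of them keep the LLN in both lines. The anemia g/L line is the only exception.

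**The case against.** The strongest reply accepts the misprint and disputes what follows from it. Most of that reply stands.

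- **Lost mandatory AEs.** A reader might infer that anemia in the mandatory range can be logged as discretionary Grade 1 and so escape reporting. The documents do not support that. A value of 90 g/L lies in the printed Grade 2 band, and section 8.4 imposes the duty on all Grade 2 and higher values, whatever other band they also meet. What remains is ambiguity in the recorded grade.
- **Unreported mild anemia.** A reader might infer that values from 100 g/L to the LLN go unreported. Section 8.4 has every out-of-range safety result reviewed by the principal investigator, requires a clinically significant one after Screening to be recorded as an AE or linked to a concomitant disease, and falls back on medical judgment where the grading scheme is not available. Grade 1 values face the same clinical-significance test, so losing the grade does not mean losing the report.
- **Wrong dataset grades.** A reader might infer that the programmed grades are wrong and must be re-run. SAP section 12.5.4.3 cites CTCAE 4.03, and nothing shows that the program reads this cell. Disagreement between site and dataset is possible but not shown.
- **Foreseeable hemoglobin falls.** The roughly 303 mL of blood in Protocol section 7.6.1 is a maximum that includes optional bio-banking. Without it, 303 − 36 − 57 = 210 mL remains, spread over the study. No figure in the documents links this to hemoglobin crossing 100 g/L.
- **Unit.** Neither Protocol section 7.5.1 nor SAP section 12.5.4.3 gives a hemoglobin unit. If the site grades in g/dL or mmol, the defect has no effect.

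It could also be said that an LLN was lost in the public PDF copy. That cannot be wholly excluded. However, the LLN survives in the other two lines of the same cell and in every comparable row, so a slip in the source table is more likely.

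**Conclusion.** The Grade 1 g/L line for anemia is inconsistent with the rest of its row. On that line, values from 100 g/L to the LLN have no grade, values from 80 to just under 100 g/L have Grades 1 and 2, and values below 80 g/L have Grades 1 and 3.

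The practical effect depends on hemoglobin being graded in g/L, which the documents leave open, so the number of affected results cannot be estimated. Given that condition, the effect is ambiguous site severity grades, an unclear worsening rule, a blurred line between discretionary and mandatory reporting, and possible mismatch with the programmed grades. It is not a loss of the Grade 2 reporting duty or of the clinical-significance review, and it does not touch any primary endpoint. The point is worth correcting because section 8.4 uses this table as a decision rule, but it is confined to safety grading.

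**What to change.** 1. Reconcile the three unit lines of the Grade 1 anemia cell so that they are conversions of one range and do not overlap Grades 2 and 3. Which bounds apply is for the sponsor to confirm against its source; none is proposed here.
2. Confirm that Appendix E, as reconciled, agrees with the scheme used by the SAP grading program.
3. Establish which unit the site used. If it was g/L, re-check the hemoglobin results graded there, including the severity of any related AE and any worsening in grade.

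The cost is one table cell, one query to the site and one check of the programming specification. Dataset grades need no re-run unless the program turns out to have used this cell.
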